Maternal sleep disruption, specifically SDB, has emerged as a predictor of poor maternal outcomes. Symptoms of SDB affect up to 15% of women at conception,^{2, 14} up to 35% of women in the 3rd trimester,^{1 2} and up to 85% of women with hypertensive disorders of pregnancy.^{4, 15} Objectively-diagnosed SDB has been found in 8% of all pregnant women by mid-gestation,¹⁶ 15% of obese pregnant women,¹⁴ and approximately half of hypertensive pregnancy women.^{4, 15} There is now a wealth of literature that demonstrates independent associations between maternal SDB and gestational hypertension, preeclampsia, and gestational diabetes.^{2, 17- 20} Maternal SDB has also been associated with FGR,^{6, 19} including a large study by our group.⁷ In some exciting and novel preliminary data we have demonstrated that APAP use in pregnancy is associated with improved infant birth weight: infants born to women who used APAP during pregnancy (n=18), compared to infants born to women with SDB who did not use APAP (n=17), have larger birth weight (3036±833g vs. 2485±1050g, p=0.08) even after accounting for duration of PAP use. In addition, we have preliminary data to show that APAP in pregnancy is associated with longer gestation; women who used APAP (n=18) continued their pregnancies for a mean of 2.5±3.4 weeks longer than those who did not use PAP (n=17; 37.7±2.8 weeks vs. 35.1±4.1 weeks, p=0.03). *This is a clinically significant duration that will have long-term impact on infant health.* Moreover, in a retrospective study we have data to show that fetuses of women with SDB have a fall in growth across the centiles, a pattern that was not present in women using APAP therapy.²¹ In a small pilot study it has recently been reported that SDB in women with preeclampsia is associated with reduced fetal movement, which was partially reversed with APAP therapy.²² Taken together, these preliminary findings suggest that APAP treatment of pregnant women with SDB is a window of opportunity to provide an urgently-needed clinical intervention that will improve fetal growth trajectory and thus have a positive impact on not only short-term pregnancy outcomes but also on longer-term morbidity.

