Potential Problems and Alternative Strategies: Although our preliminary data solidly support the hypotheses there is the possibility that no differences will be found for fetal growth trajectory. In the unlikely even that this occurs, we will examine fetal heart rate variables and subjective measures of fetal movement for any subtle signs of fetal compromise that may not translate to large enough insults to significantly affect fetal growth measures but which may aid in the understanding of fetal wellbeing. Another potential problem is that insufficient women with SDB will be identified. However, given the large pool of women (approximately 4500/year) we do not foresee problems with recruitment. Although infrequent, it is possible that women with SDB in early pregnancy may not meet the threshold later in pregnancy. To minimize this (as well as drop out for other reasons), we will over-enroll women to allow our final sample size to be sufficient for analysis (at least 27 women per group). Women could decline to undergo home monitoring; this is not likely to occur, since >50% of high and low-risk women approached for home monitoring have enrolled in our protocols. An additional potential problem is the use and adherence to APAP. However, we have previously demonstrated our ability to maintain adherence in 80% of pregnant women in a longitudinal study of APAP therapy in hypertensive pregnancies, of which about half did not even meet present criteria for SDB (K23HL095739); of those with SDB, we were able to maintain adherence in >90%. Our success was due to the ability to build a strong rapport along with frequent contact. The current study will only randomize women with SDB and thus, we believe that we are in a strong position to retain sufficient women on APAP. A further possibility exists in that no differences in gross placental pathology will be found. However, histological differences may still be present. If markers of hypoxia are not found, we will use the banked placental tissue to investigate the presence of angiogenic factors and receptors e.g., vascular endothelial growth factor, placental growth factor, and soluble fms-like tyrosine kinase 1. We will also investigate neutrophil extracellular traps as we have previously described⁴⁵ or epigenetic changes.

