Sample Size and Power Calculation: To estimate the sample size required to detect a clinically important difference between groups we calculated the difference in birth weight between newborns of women with SDB who used APAP vs. those who did not use APAP, using a linear regression model which accounted for length of APAP use. From preliminary data of n=18 APAP users and n=17 non-PAP users, the APAP users delivered infants who were 551grams (over 1 pound) larger than non-APAP users. Assuming a mean birth weight of 2485g for the SDB group and 3036g for the APAP group with a standard deviation of 625g, a sample size of n=27 per group has 90% power to detect a difference with $\alpha=0.05$. Even with a sample size of n=21 per group, we would

still have >80% power to detect this difference. We are therefore confident that our milestones will be obtained if we enroll n=30 women per group. There is ample power to detect a clinically significant endpoint.

Statement of how patients will be recruited and retained:

Recruitment: Pregnant women will be recruited from obstetric clinics as described above. Our wealth of experience in conducting sleep-related protocols with pregnant women has allowed efficient, targeted screening in order to identify those at highest risk of SDB, and reserving objective confirmatory testing to those likely to provide the highest yield of SDB diagnoses. Our preliminary data demonstrate that report of habitual snoring (snoring ≥ 3 nights per week) is an excellent marker for the presence of objectively confirmed SDB. In a group of n=67 pregnant women (mean gestational age 28.2 ± 7.8 weeks) who underwent polysomnography, mean AHI was significantly higher in habitually snoring pregnant women compared to non-snoring pregnant women (17.3 vs. 3.3; $p < 0.01$). We found that habitual snoring has good sensitivity (0.80), specificity (0.77), positive (0.70) and negative (0.90) predictive value for identifying women with confirmed SDB. Our approach thus minimizes the need for widespread objective testing. Furthermore, we have successfully treated pregnant women with APAP. Of n=51 pregnant women with SDB who were offered PAP (K23 HL095739) we enrolled n=45 women (88% of invited).

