Timetable: The time required for training staff and launch of the protocol is minimal (<1 month) due to our extensive experience in conducting APAP trials in pregnant women, together with our existing collaborations with Maternal-Fetal Medicine and Pathology. This then allows maximal time to run the protocol and enroll n=4 women per month to ensure that all women are randomized by month 17. This will allow for intervention, 3rd trimester ultrasounds, and collection of all placental tissue by month 23, prior to analysis for grant submissions (month 24).

EVALUATION: Plans for evaluation, how success will be measured and how progress/results will be documented: Successful milestones will be considered as follows: a) $\geq 95\%$ of women have good quality home sleep tests with ≥ 4 hours sleep time; b) serial fetal growth measures are obtained on $\geq 95\%$ of participants; c) for women randomized to APAP, $\geq 85\%$ of women will use APAP ≥ 4 hours per night, ≥ 4 nights/week, and d) placental tissue is obtained on $\geq 95\%$ of women. The PI and coordinator will meet twice per week to discuss progress and troubleshoot difficulties. The whole team will meet monthly. The main outcome will be longitudinal fetal growth trajectory and the secondary outcome will be placental histology. **Analytic approach:** A multi-level model will be the primary analysis method used to assess fetal growth measures over time and between groups. The model will account for the repeated collection of these measures over time Nonlinear time trends will also be

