investigated as it is hypothesized that the slope for fetal growth over time will not be as steep in the third trimester, especially for women with SDB. The model will take the general form: $y_{ij} = \beta_1 + \beta_2 x_{2ij} + \beta_{3ij} + \dots + \beta_p x_{pij} + \phi_{0j} + \epsilon_{ij}$ where y_{ij} is the fetal growth measure at visit i for participant j and ϕ_{0j} is the participant specific random intercept. β_1 through β_p are the fixed effect parameters estimated by the model and ϵ_{ij} is the time varying residual. The β coefficients associated with group membership are of primary interest. In addition to the random intercept per participant, random slopes will also be investigated for inclusion into the final model. For analysis of placental histology a Chi-square goodness of fit test will first be used to test for mean differences in the binary placental histology measurements between groups and a multivariable logistic regression will be used to assess group differences while controlling for potentially confounding polysomnographic variables (e.g., oxygen saturation nadir or AHI). We expect that the presence of SDB will slow fetal growth across the third trimester (>30% fall in centiles), a phenomenon not present with use of APAP therapy. Furthermore, we expect to demonstrate decreased fetoplacental weight ratio, increased chorangiosis (hypoxia), and increased vasculopathic inflammation in SDB placentas, phenomena not observed with use of APAP therapy. These data will show that maternal SDB exerts an effect on the fetus that is at least partially reversible with APAP therapy.

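### The 90% power figure rests on an unsourced SD of 625 g that conflicts with the plan's own pilot (about 56% power at 27 per group), and no power or precision is given for the main outcome

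*Combined protocol and SAP*

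**What the plan says.** The section Sample Size and Power Calculation takes its effect from a pilot of 18 APAP users and 17 non-users, "using a linear regression model which accounted for length of APAP use". It continues: "Assuming a mean birth weight of 2485g for the SDB group and 3036g for the APAP group with a standard deviation of 625g". It gives 90% power for 27 per group at alpha 0.05, says that with 21 per group the trial would "still have >80% power to detect this difference", plans to enrol 30 per group, and concludes: "There is ample power to detect a clinically significant endpoint".

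The Background section describes the same pilot: infants of APAP users "have larger birth weight (3036±833g vs. 2485±1050g, p=0.08) even after accounting for duration of PAP use". It also reports that users delivered a mean of 2.5 weeks later than non-users.

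Potential Problems and Alternative Strategies relies on the same target: "we will over-enroll women to allow our final sample size to be sufficient for analysis (at least 27 women per group".

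The Evaluation section says: "The main outcome will be longitudinal fetal growth trajectory and the secondary outcome will be placental histology". Under Analytic approach, the primary analysis is a multi-level model of the repeated fetal measures, in which the "coefficients associated with group membership are of primary interest".

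**The concern.** There are two separate faults.

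**The SD.** The means and the 551 g difference come from the pilot, but the SD does not. The value used, 625 g, is below both pilot SDs, and the plan neither cites a source for it nor explains the gap. Power depends heavily on this input.

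**The endpoint.** The calculation concerns raw birth weight, while the main outcome is growth trajectory from scans at 28, 32 and 36 weeks. Birth weight cannot stand in for it. Users in the pilot delivered later, so part of the 551 g may be longer gestation, which those scans do not measure.

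The interpretation of the trial is at stake. A reader of a null result would believe it came from a study with 90% power, when the plan's own data do not support that for birth weight and nothing is stated for the outcome that matters most.

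**Working it through.** **Inputs.** Means 3036 g and 2485 g, difference 551 g (Background; Sample Size). Planning SD 625 g (Sample Size). Pilot SDs 833 g (n=18) and 1050 g (n=17), p=0.08 (Background; ± read as SD). Alpha 0.05; sidedness is not stated. Two-sided is assumed because it reproduces the plan's figures, whereas one-sided would give 94.5% at n=27.

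**Step 1: reproduce the plan.** The normal formula is power = Φ(551 / (SD × √(2/n)) − 1.96). With SD 625:
- n=27: Φ(3.239 − 1.96) = 0.900
- n=21: Φ(2.857 − 1.96) = 0.815

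The stated figures follow from 625 g. A t-test (noncentral t) gives 0.889 and 0.796.

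**Step 2: the pilot SD.** Pooled SD = √((17 × 833² + 16 × 1050²)/33) = √((11.80M + 17.64M)/33) = 944 g. The 95% CI (chi-square, 33 df, assuming normality and a common variance) is 762 to 1243 g.

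**Step 3: power for raw birth weight**, two-sided t-test, 551 g taken as true:

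| SD (g) | Basis | n=21 | n=27 | n=30 |
|---|---|---|---|---|
| 625 | plan | 80% | 89% | 92% |
| 762 | lower limit of pooled SD | 63% | 74% | 79% |
| 833 | user arm SD in both arms | 55% | 66% | 71% |
| 944 | pooled pilot SD | 45% | 56% | 60% |
| 1050 | non-user arm SD in both arms | 38% | 47% | 52% |
| 1243 | upper limit of pooled SD | 29% | 36% | 39% |

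Allowing unequal variances (833 and 1050 g) gives 45%, 55% and 60%.

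**Step 4: precision.** The 95% CI half-width at n=27 is t(52) × SD × √(2/27). This is 2.007 × 944 × 0.272 = 516 g at the pilot SD and 341 g at 625 g. At 944 g, the difference detectable with 90% power is 849 g at n=27 and 804 g at n=30.

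**Step 5: could adjusting for length of APAP use give 625 g?** It is the only adjustment the plan names. Assume non-users are coded zero. Length of use then explains none of the variation among them, and their sum of squares stays at 16 × 1050² = 17.64M. A residual SD of 625 g on 32 df allows only 625² × 32 = 12.50M. The smallest possible residual SD is √(17.64M/32) = 742 g, even if length explained all variation among users. If it explained half, the figure is √((17.64M + 5.90M)/32) = 858 g. These numbers only bound the adjusted pilot model; they are not SDs available to the randomized comparison.

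**Step 6: the pilot p-value.** With SD 625 g at 18 vs 17, SE = 625 × √(1/18 + 1/17) = 211 g, t = 2.61 and p = 0.014. The pilot SDs give t = 1.73 and p = 0.094. The reported p=0.08, read as a t-test of 551 g, implies t = 1.81, SE = 305 g and an effective SD of 902 g (60% power at n=27). This is supporting evidence only, because p=0.08 may come from the adjusted model, where overlap between group and length of use also enlarges the SE.

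**Step 7: the main outcome.** The documents give no effect size, SD or within-woman correlation for fetal growth at 28, 32 and 36 weeks. Power for it cannot be computed from them.

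**The case against.** The strongest defence is that 625 g may be a sensible planning value for a less variable population. The pilot pregnancies ended at widely varying gestations (35.1±4.1 and 37.7±2.8 weeks), which widens birth-weight SDs. The trial excludes smokers and does not randomize women with severe SDB or severe sleepiness. Other covariates could also lower the residual SD. This is possible, but the plan argues none of it. A different population or model might also change the 551 g, so the pilot difference cannot simply be kept beside a smaller SD.

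A second objection is that p=0.08 proves little. If it comes from the adjusted model, collinearity could produce it with a residual SD of 625 g; a variance inflation factor of about 2.1 would do so. That is fair as far as it goes. But the argument codes non-users as zero, and step 5 shows that this coding rules out a residual SD below 742 g in these data. The case rests on the SDs and does not need the p-value.

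Third, 56% is only one point in a wide range, and it takes 551 g as true although the pilot's unadjusted 95% CI is about −99 to 1201 g. Excluding 625 g also depends on pooling: the user arm alone gives 625 to 1249 g, the non-user arm 782 to 1598 g. All of this stands, so the range should accompany the figure. It does not rescue an unqualified 90%.

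Finally, the fault lies in an input and in the choice of endpoint, not in the arithmetic, and low power for the main outcome has not been shown. Both points are correct.

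**Conclusion.** The concern holds. The 90% and >80% figures depend on an SD of 625 g that has no source and conflicts with the pilot that supplied the means. At the pooled pilot SD, power for a true 551 g difference in raw birth weight is 45%, 56% and 60% at 21, 27 and 30 per group. Over the SD's 95% CI it is 29–63%, 36–74% and 39–79%. Even the smaller pilot SD gives only 66% at 27. These figures assume a two-sided t-test at 0.05, normality, a common variance for the SD interval, and the full 551 g as the true effect.

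Independently of the SD, the plan states no power or precision for its main outcome, and would still lack it if 625 g were fully justified. Whether the trial is well or poorly powered for growth trajectory is unknown.

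**What to change.** This needs correcting before the power statement is relied on or reported.

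1. In Sample Size and Power Calculation, replace the power statement with: *Using the preliminary pooled SD of 944 g, a two-sided t-test for a true raw birth-weight difference of 551 g has about 56% power with 27 per group and 60% with 30 (36–74% and 39–79% over the 95% CI of the pooled SD, 762–1243 g, assuming normality and a common variance). Birth weight is not the main outcome.* Alternatively, give and justify a source for 625 g together with the difference that belongs with it.
2. Remove the closing claim of ample power.
3. In Potential Problems and Alternative Strategies, call 27 per group a feasibility target, or re-derive it.
4. Add power or expected confidence-interval width for the group effect in the planned multi-level model with scans at 28, 32 and 36 weeks, stating the assumed SD and within-woman correlation. If the team's data cannot supply these, state them as assumptions and show a range.

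The cost is rewording in two sections and one short calculation. The stated power will look less favourable. Enrolment, visits and analysis do not change.

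### The stated power makes no allowance for the non-adherence the plan's own milestone accepts: at 85% adherence, 90% at n=27 becomes about 77–79% if non-adherers gain nothing and 84–85% if they gain half

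*Combined protocol and SAP*

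**What the plan says.** All references are to the combined protocol and SAP.

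- **Source of the effect** (Sample Size and Power Calculation): "From preliminary data of n=18 APAP users and n=17 non-PAP users", the plan takes a birth-weight difference of 551 g between users and non-users.
- **Planning values** (same section): "Assuming a mean birth weight of 2485g for the SDB group and 3036g for the APAP group", "with a standard deviation of 625g", alpha 0.05.
- **Stated power** (same section): "a sample size of n=27 per group has 90% power to detect a difference". For the smaller size: "Even with a sample size of n=21 per group, we would" "still have >80% power to detect this difference". Planned enrolment is 30 per group.
- **Adherence target** (Evaluation, milestone c): "for women randomized to APAP", success means that at least 85% use the device for at least 4 hours a night on at least 4 nights a week.
- **Adherence as a risk** (Potential Problems and Alternative Strategies): it is named as a problem and answered with past experience, namely 80% in an earlier cohort of hypertensive pregnancies and more than 90% among women with SDB. Over-enrolment, to keep at least 27 per group, is tied to women who no longer meet the SDB threshold and to drop-out.
- **Comparison** (Analytic approach): the coefficients for group are of main interest. No intention-to-treat population is defined, and no rule covers women assigned to APAP who do not use it.

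**The concern.** A difference between users and non-users is the effect of use, at best. A difference between randomised groups is the effect of assignment, and it shrinks when some assigned women do not use the device. The plan accepts up to 15% of the APAP group below its use threshold, yet its power figures carry the user effect over unchanged. Nothing else in the plan covers the gap, because the enrolment margin is reserved for other losses.

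At stake is how a null result would be read. The section concludes that power is ample, and the plan presents the randomised design as a main strength. If power for the randomised comparison of birth weight is nearer 80% than 90%, a non-significant result is weaker evidence against a 551 g effect of use than the plan implies.

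**Working it through.** **Inputs from the documents.** Means 2485 g and 3036 g, so d = 3036 − 2485 = 551 g. SD 625 g. Alpha 0.05; sidedness is not stated, but two-sided reproduces the plan and one-sided does not (94% at n=27). Group sizes 27 and 21, with 30 enrolled. Adherence floor 85%; past adherence in women with SDB above 90%.

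**Input not in the documents.** The effect in women below the threshold, written as a fraction f of 551 g. I show f = 0 to 0.75.

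**Formulas.** SE = 625 × √(2/n). Normal approximation: power = Φ(d/SE − 1.96). t-test: noncentral t with 2n − 2 degrees of freedom and noncentrality d/SE, two-sided.

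**Step 1: the plan's own figures, at 551 g.**
- n=27: SE = 170.1, d/SE = 3.239, Φ(1.279) = 90.0%. By t-test, 88.9%.
- n=21: SE = 192.9, d/SE = 2.857, Φ(0.897) = 81.5%. By t-test, 79.6%.

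The plan's statements fit the normal approximation, so I keep both methods throughout and compare like with like.

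**Step 2: dilution.** With adherence a, expected difference = 551 × (a + (1 − a) × f).
- a = 0.85, f = 0: 0.85 × 551 = 468 g. At n=27, 468.35/170.1 = 2.753 and Φ(0.793) = 78.6%.
- a = 0.85, f = 0.5: 0.925 × 551 = 510 g.
- a = 0.90, f = 0: 0.90 × 551 = 496 g.

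| Case (SD 625 g) | Difference | n=27: t / normal | n=21: t / normal |
|---|---|---|---|
| Full adherence | 551 g | 88.9% / 90.0% | 79.6% / 81.5% |
| 90%, no benefit in the rest | 496 g | 81.6% / 83.0% | 70.9% / 72.9% |
| 85%, half benefit in the rest | 510 g | 83.7% / 85.0% | 73.2% / 75.3% |
| 85%, no benefit in the rest | 468 g | 77.1% / 78.6% | 65.9% / 68.0% |

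At 85% with 25% or 75% of the benefit in the rest, the t-test gives 80.6% or 86.4% at n=27, and 69.6% or 76.5% at n=21.

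**Step 3: the enrolled size.** At n=30 with nobody lost, the 85% zero-benefit case gives 81.4% (t) or 82.7% (normal). Restoring 90% in that case would take 39 (t) or 38 (normal) per group.

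**Step 4: how much slack the statements have.** At n=27 the normal figure is 89.96% at the full effect, so any dilution takes it below 90%. At n=21, 80% needs d = (1.96 + 0.842) × 192.9 = 540 g, which is 98% of 551 g. A dilution of about 2% is enough to lose the 80%.

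**Sensitivity.** A mixture of adherers and non-adherers also widens the spread in the APAP group, to a pooled SD of about 640 g in the 85% zero-benefit case. The t-test figures then become 75.1% at n=27 and 63.8% at n=21.

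**The case against.** The strongest case on the other side has five parts.

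1. *The arithmetic is right.* The plan claims power for 551 g, and for 551 g the figures reproduce. This stands. A reader might infer a calculation error, and there is none; what is missing is an allowance.

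2. *Zero benefit is not in the documents.* Women below 4 hours on 4 nights may be partial users. This stands too. A reader might take 77% and 66% as the trial's actual power, but those are t-test values that also require no benefit in every woman below the threshold. Setting them against 90% and 81.5% from the normal approximation would add 1 to 2 points of apparent loss that come only from the change of method.

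3. *551 g may already be diluted.* The plan does not say whether all 18 preliminary users met the threshold. If some did not, multiplying by 0.85 counts part of the non-adherence twice. This cannot be excluded. But the plan does not claim it, and adjusting the preliminary comparison for length of use is not an allowance for non-use in the trial.

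4. *85% is a floor, and 30 women per group are enrolled.* The team reports more than 90% adherence in women with SDB; the 80% figure comes from a cohort of which about half did not meet SDB criteria. At 90%, n=27 still has 82–83% even with no benefit in the rest. At n=30, the 85% zero-benefit case has 81–83%, but the plan has already assigned that margin to drop-out and loss of SDB.

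5. *Non-adherers could be left out.* With 0.85 × 27 ≈ 23 against 27 at 551 g, the t-test gives 86%. That is still below 90% and gives up the randomised comparison.

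Parts 1 to 4 narrow the point to a conditional range. None of them supplies the missing allowance.

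**Conclusion.** The point holds as an unstated assumption in the power statement. The 90% and the figure above 80% belong to full adherence, and the plan's own success criterion accepts less. At the 85% floor, analysed as randomised, n=27 gives about 77–79% to 84–85% as the benefit in non-adherers goes from none to half. For n=21 the corresponding figures are 66–68% and 73–75%. The claim at n=27 weakens moderately. The claim at n=21 fails in every diluted case shown and, on a t-test, falls just short (79.6%) even with full adherence.

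The size rests on three things: the plan's SD of 625 g, the assumed benefit below the threshold, and 551 g being the effect in adherent women.

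Two stronger readings are not supported. The documents do not show that the trial is underpowered by any conventional standard, since 80% or more remains plausible at n=27 to 30. Nor are these figures the power of the main analysis: they concern birth weight, while the named main outcome is the fetal growth trajectory, for which the plan gives no power calculation.

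**What to change.** Amend the Sample Size and Power Calculation section so that it:

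- says the power refers to women compared as randomised;
- gives the range with its assumption: at 85% adherence and SD 625 g, about 77–79% at n=27 and 66–68% at n=21 if women below the threshold gain nothing, and about 84–85% and 73–75% if they gain half; at 90% adherence with no benefit in the rest, about 82–83% and 71–73%;
- keeps the 551 g figures, labelled as the full-adherence best case, with the method named: 90.0% and 81.5% by normal approximation, 88.9% and 79.6% by t-test;
- no longer presents more than 80% at n=21 as the power of the randomised comparison;
- notes that 30 per group gives about 81–83% in the 85% zero-benefit case only if nobody is lost, and that this margin is already assigned to drop-out and loss of SDB;
- states that all these figures are for birth weight, not for fetal growth trajectory.

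The cost is wording only. The stated power is less favourable, and enrolment does not change.
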